Safety outcomes. We will collect the following before the iTBS sessions: hours of sleep, UDS/TLFB, breathalyzer, the AE/SAE form, pain, and the Cocaine Selective Severity Assessment (CSSA – a measure of withdrawal). The AE/SAE form and pain will also be completed after the iTBS session. See Table 2 for the Study Visit Timeline.

[figure not shown]

Table 2. Study Visit Timeline – Pilot Study

[figure not shown]
Assessment	Length of Time	Details
Assess safety:	5-10 min	UDS, TLFB, pregnancy, sleep, CSSA, C-SSRS, AE/SAE form
Cognitive Assessment	10 min	MoCA
Fit EEG cap:	30 min	Measure & place cap on head, gel electrodes
Complete EEG Session 1:	35 min	Resting EEG, Doors Task, Picture Viewing Task
Assess rMT:	10 min	Collect resting motor threshold
iTBS Session 1:	3 min	iTBS to dmPFC or sham iTBS
Rest:	15-20 min	Sit quietly
iTBS Session 2	3 min	iTBS to dmPFC or sham iTBS
Assess safety:	5-10 min	AE/SAE form
Cognitive Assessment	10 min	MoCA
Complete EEG Session 2:	35 min	Resting EEG, Doors Task, Picture Viewing Task

Main Trial

Design. The proposed study will use a within-subjects cross over design as shown in *Fig 2*. Non-treatment-seeking adults with a primary CUD diagnosis (N = 75) will complete screening and baseline assessments prior to completing three separate iTBS days (sham, dlPFC iTBS, or dmPFC iTBS), order counterbalanced across participants. On each day, EEG will be collected before and after 3 iTBS successive sessions (15-minutes between sessions). Days will be spaced at least 24-hours apart and will be completed within 2 weeks. We will aim to consent 115 participants to achieve 75 completed.

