Modeling Assumptions. Evaluation of assumptions for frequentist models will use graphical evidence (e.g., residual plots) and formal statistical tests. Bayesian convergence and modeling assumptions will be evaluated by effective sample size, scale reduction factors ("rhat"), and posterior predictive checking. Violated assumptions will be addressed via model re-specification, variable transformation, robust estimation, stratification, and/or coefficient scaling where appropriate. **Intention-to-treat (ITT)** primary analyses will include all randomized participants; follow-up analyses may evaluate modified ITT samples should specific participants merit exclusion (e.g., randomized but never initiated the trial). A per protocol analysis will complement the primary ITT analysis as due diligence. **Missing data** patterns will be evaluated using Little's Test of Missing Completely at Random (MCAR)¹³⁶ for continuous outcomes and the Park and Lee approach¹³⁷ for discrete outcomes. Models will handle missingness via maximum likelihood, explicit modeling of missingness¹³⁸, and/or imputation with sensitivity analyses to evaluate the robustness of findings. Each approach is

robust to ignorable missingness (i.e., missing completely at random and missing at random). Pattern-mixture modeling will be used to address identified non-ignorable missing data patterns¹³⁹.

Specific Analyses

All statistical models (described below) will account for correlated observations via the best-fitting structure of random effects (i.e., lowest information criteria) found when fitting level-2 intercepts and/or slopes) for repeated measures (where necessary) and statistically control for potential confounders as defined above. Outcome variables will be modeled as difference scores to account for the pre/post design (i.e., post-iTBS minus pre-iTBS).

Hypothesis 1a (Primary): Active iTBS relative to sham will increase the amplitude of the RewP/delta power to rewards compared to non-rewards. GLMM will model the change in amplitude of the RewP/delta power to rewards as a function of iTBS condition, with random effects to account for repeated measures.

Hypothesis 1b (Exploratory): iTBS to dmPFC will result in a greater increase in the RewP/delta power compared to dPFC. Follow-up testing of the model described above for Hypothesis 1a will evaluate pairwise comparisons between iTBS conditions.

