Hypothesis 2a (Primary): Active iTBS relative to sham will switch the drug>pleasant LPP bias. GLMM will model the change in LPP bias as a function of iTBS condition.

Hypothesis 2b (Exploratory): iTBS to dmPFC will result in a greater increase in LPP bias (i.e., greater LPP to pleasant images compared to cocaine images). Follow-up testing of the model for Hypothesis 2a will evaluate pairwise comparisons between iTBS conditions.

Hypothesis 3a (Exploratory): Analyses will explore baseline CUD severity, impulsivity, and craving as predictors of iTBS effects on EEG. GLMM will model EEG outcomes as a function of the interaction between iTBS condition and each named predictor (in separate models): baseline CUD severity, impulsivity, and craving, controlling for constituent main effects.

Sample Size and Power Analysis

The current proposal is powered with respect to the primary hypothesis in the study (Hypothesis 1a). G*Power v. 3.1.9.4 provides calculations from the frequentist perspective via a within-factor repeated measures model, a simplified version of the GLMM described above. Assuming a correlation among repeated measures $r = 0.50$ and two-tailed $\alpha = 0.05$, the current feasible sample size $N = 75$ provides 80% power to detect an effect size as small as Cohen's $f = 0.149$ (comparable to a small-to-moderate Cohen's $d = 0.30$). These estimates also broadly apply to Hypothesis 2a. Bayesian analyses proposed above will then provide a complementary analysis of all models that yields probabilistic estimates for all model effects, even in the context of relatively smaller sample sizes¹⁴⁰ (i.e., the available data for subgroup analyses or higher-complexity models).

Protection of Human Subjects

Inclusion Criteria:

1. be between 18 and 65 years of age at the time of the first study visit (iTBS session day)
2. meet DSM-5 criteria for current cocaine use disorder of at least moderate severity (≥ 4 symptoms)
3. have at least 1 positive urine BE specimen (≥ 300 ng/mL) during intake
4. be able to understand the consent form and provide written informed consent
5. be able to provide the following verifiable information for a minimum of 2 contact persons: full legal name, email address, local mailing address, and as applicable, home, work, and cell phone numbers

Exclusion criteria:

1. current DSM-5 diagnosis for substance use disorder (of at least moderate severity) other than cocaine, marijuana, or nicotine

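### Main-trial Hypotheses 1a and 2a compare active iTBS with sham, but no active-versus-sham contrast is named as the primary test, and the stated 80% power belongs to a three-level omnibus test

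*Combined protocol and SAP*

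**What the plan says.** All of this concerns the main trial, which the cover page says is registered separately from the five-person pilot.

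- **Design (Study design, Main Trial).** Each participant completes "three separate iTBS days (sham, dlPFC iTBS, or dmPFC iTBS), order counterbalanced across participants". The condition factor therefore has three within-person levels.
- **Hypothesis 1a (Specific Analyses).** "Hypothesis 1a (Primary): Active iTBS relative to sham will increase the amplitude of the RewP/delta power to rewards compared to non-rewards". The analysis: "GLMM will model the change in amplitude of the RewP/delta power to rewards as a function of iTBS condition", with random effects for the repeated measures. The outcome is the post-minus-pre change, so each condition gives one value per person.
- **Hypothesis 2a.** "Hypothesis 2a (Primary): Active iTBS relative to sham will switch the drug>pleasant LPP bias". The analysis: "GLMM will model the change in LPP bias as a function of iTBS condition".
- **Hypothesis 1b, exploratory.** "Follow-up testing of the model described above for Hypothesis 1a will evaluate pairwise comparisons between iTBS conditions". Hypothesis 2b, also exploratory, has the same provision for LPP bias.
- **Multiplicity (Probability and Inference).** Primary outcomes are tested at two-tailed 0.05. Exploratory and post hoc analyses fall under false discovery rate control.
- **Power (Sample Size and Power Analysis).** The trial is powered for Hypothesis 1a "via a within-factor repeated measures model, a simplified version of the GLMM described above". With r = 0.50 and alpha 0.05, N = 75 is said to give 80% power for f = 0.149. The figure is said to apply broadly to Hypothesis 2a. The number of repeated measurements entered is not stated.

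For 1a and 2a the plan states no pooling of the active sites, no reference coding, no contrast and no decision rule.

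**The concern.** Active versus sham is a one-degree-of-freedom, signed question. An overall effect of a three-level factor is a different question: it asks whether the three means differ in any way. It can be significant because the two active sites differ from each other, or because stimulation lowers the RewP. The comparisons with sham that would answer 1a and 2a are mentioned only inside the exploratory tier.

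Two things are at stake. First, the power figure attached to Hypothesis 1a may describe a test other than the one that answers it. Second, with no deciding contrast stated, the choice remains open after the data are seen: overall test, pooled active versus sham, dlPFC versus sham, dmPFC versus sham, or both sites. A difference between sites is not remote, since Hypothesis 1b predicts one.

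**Working it through.** **Inputs from the plan:** N = 75, r = 0.50, alpha = 0.05, f = 0.149, three conditions. **Assumed:** the pattern of condition means, because the documents give none; equal variances and correlations across conditions. Effects are in SD units of the change score.

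**1. Reproduce the stated power.** For a within-person factor with m levels, λ = N × m × f² / (1 − r), with df m − 1 and (N − 1)(m − 1).

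For m = 3: λ = 75 × 3 × 0.149² / 0.50 = 9.99, df 2 and 148.

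| Levels m | λ | Power |
|---|---|---|
| 2 | 6.66 | 72.1% |
| 3 | 9.99 | 80.7% |
| 4 | 13.32 | 87.3% |
| 6 | 19.98 | 94.9% |

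Only m = 3 matches the stated 80% (its detectable f at exactly 80% is 0.148). A two-level active-versus-sham test would need f = 0.164. The powered test is therefore the 2-df effect of all three conditions.

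**2. Power for active versus sham.** Take the contrast: mean of dlPFC and dmPFC, minus sham.

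SE = √[1.5 × (1 − r) / N] = √(1.5 × 0.50 / 75) = 0.100 SD. Power comes from a noncentral t with 148 df, two-sided 0.05.

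If both sites differ from sham by the same amount d, then f = d × √2 / 3, so f = 0.149 gives d = 0.316 SD. The contrast's noncentrality is 0.316 / 0.100 = 3.16. The omnibus λ for any pattern is N × Σ(mean − grand mean)² / (1 − r).

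| Assumed difference from sham at the two sites (SD) | Pooled difference | Omnibus power | Contrast power |
|---|---|---|---|
| 0.316 and 0.316 | 0.316 | 80.7% | 88.1% |
| 0.237 and 0.316 (three quarters) | 0.277 | 71.5% | 78.5% |
| 0.158 and 0.316 (half) | 0.237 | 67.8% | 65.4% |
| 0 and 0.316 (one site only) | 0.158 | 80.7% | 34.9% |
| −0.18 and +0.18 (opposite) | 0 | 80.7% | 5.0% |

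The omnibus power is also 80.7% if both sites lower the outcome by 0.316 SD, the reverse of Hypothesis 1a. The pooled difference detectable with 80% power is 0.28 SD.

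**3. One site versus sham.** SE = √[2 × (1 − r) / N] = √(2 × 0.50 / 75) = 0.115 SD. At 0.316 SD the noncentrality is 2.74 and the power 77.6% at unadjusted two-sided 0.05. If each of two such tests used 0.05 / 2 = 0.025, the same noncentrality gives about 68%.

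**4. How often the two tests disagree.** In 20,000 simulated trials per pattern, the omnibus was significant without the pooled contrast in under 1% (equal effects), about 2% (three quarters), 9% (half), 47% (one site only) and 75% (opposite).

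**The case against.** The strongest reply is that the plan never says an overall test decides anything. It names no F test, coding or decision rule. The analysis sentence sits directly under a hypothesis worded as active versus sham, and the fitted model can yield that comparison. The follow-up pairwise tests include each site against sham, and Bayesian posteriors for the model effects would show sign and size. This stands in part. It rules out saying that the plan commits to an omnibus decision rule. It does not supply a primary contrast: the pairwise tests are exploratory, and no contrast is named for the posterior probabilities either.

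A reader might infer that a significant primary result would probably be spurious, pointing to 80.7% against 5% in the opposite-directions case. The documents do not support that. The Background cites RewP effects from stimulating dlPFC, suggests dmPFC may be better, and expects both sites to affect the LPP. That implies effects in the same direction, where the two tests seldom disagree unless one site does almost nothing. The opposite case shows what the test can respond to; it is not a forecast.

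A reader might also infer that 75 participants are too few. That is not shown either: with equal site effects the contrast has more power than the omnibus test, and 60 participants would give it 80%.

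Finally, the wording does not settle whether active means the two sites pooled or each site separately. Pooling is the more direct reading, but not the only one.

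**Conclusion.** The concern holds as a mismatch between hypothesis, named analysis and power figure. Hypotheses 1a and 2a ask about active versus sham; no such contrast is specified for them; and the 80% stated for 1a belongs to a non-directional 2-df test. That last step rests on reproducing the figure, since the number of measurements is not written down, but no other number of levels tried fits.

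The true power for active versus sham depends on the pattern of means. At N = 75 and r = 0.50 it runs from about 88% (both sites at 0.316 SD) through 78% and 65% (one site at three quarters or half of that) to 35% (one site only). These patterns are assumptions. The mismatch itself does not depend on them. The pilot is not affected: its comparison has only dmPFC and sham.

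**What to change.** State in Specific Analyses that Hypotheses 1a and 2a are each decided by one signed, sham-referenced contrast from the mixed model already planned. The most direct choice is the mean of dlPFC and dmPFC minus sham, with each site versus sham reported alongside. If the sponsor prefers, each site versus sham can be primary, with a stated multiplicity rule. Use the same contrast for the posterior probabilities.

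In Sample Size and Power Analysis, restate the power for the chosen contrast and give the pattern of condition means assumed.

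The cost is a sentence or two and a recalculation, with no new data or visits. The drawback is that the pooled contrast has little power if only one site works (35% in the case above). Separate site tests avoid that dilution but have about 78% power each at 0.316 SD before adjustment, and less after it.

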The current study will provide critical preliminary data for a larger clinical trial that will test the effects of iTBS to the dlPFC and iTBS to the dmPFC compared to sham on both cocaine use and physiological measures of reward functioning. The pilot study will focus on assessing the effects of dmPFC alone, as prior studies have already indicated that iTBS to the dlPFC can alter EEG^{91,92}. We hypothesize that reward sensitivity and cue reactivity, as measured by RewP and LPP, respectively, will demonstrate utility as biomarkers of TMS effects. There is an urgent need to improve treatments for CUD in the wake of recent trends indicating rising cocaine use and overdose deaths⁹³. Research indicates that a decreased RewP to wins and increased LPP to cocaine cues are potential targetable physiological patterns for TMS manipulation. This proposal is significant because it will 1) establish feasibility of a novel stimulation site utilizing a biomarker approach and 2) lay the ground work for a future larger clinical trial comparing the novel site to a traditional site and sham. For the main study, we will compare the effects of dmPFC to dlPFC and sham. We hypothesize that dmPFC compared to dlPFC or sham will lead to greater changes in EEG measures of reward functioning (i.e., RewP and LPP).

Aims and Hypotheses

Pilot Study

Specific Aim 1: To assess the effects of active iTBS to dmPFC on EEG measures of reward sensitivity and cue reactivity.
Hypothesis 1a: Primary hypothesis: iTBS will increase the amplitude of the RewP and switch the drug>pleasant LPP bias to pleasant>drug compared to sham iTBS.

Specific Aim 2: To assess the effects of active iTBS to dmPFC on cocaine craving in cocaine users.

Hypothesis 2a: Primary hypothesis: iTBS to dmPFC compared to sham iTBS will reduce cocaine craving (Minnesota Cocaine Craving Scale) in cocaine users.

Primary Outcome Measures

1. Reward sensitivity as assessed by the Reward Positivity – the RewP is an EEG component that will be measured immediately before and immediately following iTBS sessions on the test day.
2. Cue reactivity as assessed by the Late Positive Potential to drug vs. pleasant cues – the LPP is an EEG component that will be measured immediately before and immediately following iTBS sessions on the test days.

Secondary Outcome Measures

1. Craving – craving will be assessed immediately before and immediately following iTBS sessions on the test days.

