2. Pain – pain will be assessed via a Visual Analogue Scale (1-10) immediately before and immediately following iTBS sessions on the test days.
3. Cognitive function – a brief assessment of cognitive function will be included immediately before and after the iTBS sessions on the test days.

Main Trial

AIM 1: Assess effects of iTBS to left dlPFC and dmPFC compared to sham on reward sensitivity.

Primary Hypothesis 1a: Active iTBS relative to sham will increase the amplitude of the RewP/delta power to rewards compared to non-rewards.

Exploratory Hypothesis 1b: iTBS to dmPFC will result in a greater increase in the RewP/delta power compared to dlPFC.

AIM 2: Assess effects of iTBS to left dlPFC and dmPFC compared to sham on motivated attention.

Primary Hypothesis 2a: Active iTBS relative to sham will switch the drug>pleasant LPP bias.

Exploratory Hypothesis 2b: iTBS to dmPFC will result in a greater increase in LPP to pleasant images.

EXPLORATORY AIM 3: Identify individual differences in iTBS response with baseline characteristics.

Exploratory Hypothesis 3a: We will explore CUD severity, impulsivity, and craving as predictors of iTBS effects.

Primary Outcome Measures

1. Reward sensitivity as assessed by the Reward Positivity – the RewP is an EEG component that will be measured immediately before and immediately following iTBS sessions on the test day.
2. Cue reactivity as assessed by the Late Positive Potential to drug vs. pleasant cues – the LPP is an EEG component that will be measured immediately before and immediately following iTBS sessions on the test days.

Secondary Outcome Measures

1. Craving – craving via the Minnesota Cocaine Craving scale will be assessed immediately before and immediately following iTBS sessions on the test days.
2. Pain – pain will be assessed via a Visual Analogue Scale (1-10) immediately before and immediately following iTBS sessions on the test days.
3. Cognitive function – a brief assessment of cognitive function will be included immediately before and after the iTBS sessions on the test days.
4. Behavioral reward learning – participants will complete the Pavlovian Go/No-Go task before and after iTBS sessions.
5. Anhedonia – the Snaith Hamilton Pleasure Scale (SHAPS) will be collected before and after iTBS sessions.

Study design

Pilot Study

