Concomitant Medications Tracking Log	X	X	X	X
Columbia Suicidal Severity Rating Scale (C-SSRS)	X	X	X	X
Danger Assessment Tool	X	X	X	X
Cocaine Selective Severity Assessment (CSSA)		X	X	X
Hours of Sleep		X	X	X
TMS Side Effects Questionnaire*		X	X	X
Pain Visual Analogue Scale (VAS)*		X	X	X
Montreal Cognitive Assessment (MoCA)*		X	X	X
TMS				
Intermittent theta burst stimulation 3x with 15-minute intervals in between		X	X	X
Study Manipulation Measures				
Blinding Question		X	X	X
Main Outcomes				
EEG (Doors Task & Picture Viewing		X	X	X

Task)*				
Behavioral Reward (Pavlovian Go/No-Go)*		X	X	X
Other Measures/Outcomes				
Minnesota Cocaine Craving Scale (MCCS)*	X	X	X	X
Snaith-Hamilton Anhedonia Scale (SHAPS)*	X	X	X	X
Cocaine Use Timeline Follow Back (TLFB)	X	X	X	X
Barratt Impulsiveness Scale (BIS-11)	X			
PROMIS Sleep Disturbance/Impairment		X	X	X
Profile of Mood States (POMS)		X	X	X
Delay Task*		X	X	X
Cocaine Purchasing Task	X			

¹dorsolateral prefrontal cortex; ²dorsomedial prefrontal cortex; * measured before and after TMS

EEG Measures. During the tasks described below, EEG will be collected using a 64-channel actiCAP electrode cap, amplified with BrainAmp MR and digitized using Brain Vision Recorder (Brain Products, Munich). Impedances will be maintained below 50 k(OHM). The sampling rate will be 500 Hz and data will be filtered with .1 Hz high-pass and 100 Hz low-pass filters. Data reduction will be performed with Brain Vision Analyzer 2, MATLAB, and BESA. Both ERP (mean amplitude) and TFA approaches will be used to analyze the RewP. While the main hypotheses will look at delta power, we will also examine changes in other frequencies, including theta, in exploratory analyses. The LPP will be defined as the mean amplitude between 400-800ms post stimulus^{47,81} and a difference score (cocaine minus pleasant) will be used to assess LPP bias.

Reward Sensitivity. The Doors Task⁵⁹ will be used to elicit the RewP. Participants guess which door contains a reward behind it. After selecting a door, the participants are notified if they won by a green arrow pointing up or if they lost by a red arrow pointing down. Unknown to the participants, winning and losing outcomes are presented 50% of the time in a random order. Self-reported anhedonia (Snaith Hamilton Pleasure Scale; SHAPS) will also be assessed at each visit as a secondary measure of reward sensitivity.

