Specific Analyses. *Aim 1.* iTBS to dmPFC compared to sham will increase the amplitude of the RewP and switch the drug>pleasant LPP bias to pleasant>drug. GLM will model RewP amplitude as a function of time (pre vs. post iTBS session) and location (dmPFC or sham). GLM will model LPP amplitude as a function of time (pre vs. post iTBS sessions), condition (i.e., image type [pleasant, unpleasant, cocaine, and neutral]), and location (dmPFC or sham). *Aim 2.* iTBS will reduce cocaine craving (Minnesota Cocaine Craving Scale). GLM will model craving as a function of time (pre vs. post

iTBS sessions) and location (dmPFC or sham). *Non-Primary Measures*. Secondary analyses will also model pain and MoCA scores as a function of time (pre vs. post iTBS sessions) and location (dmPFC or sham).

Sample Size and Power Analysis. The current pilot study is focused on evaluating the feasibility of the current approach with respect to recruitment, retention, assessment procedures, and implementation. Although preliminary statistical analyses will evaluate the magnitude of any changes observed over time, these are not expected to provide a meaningful estimate that would generalize beyond the small sample observed here. By providing evidence for feasibility, the present study will inform a subsequent study with formal hypothesis testing. This approach to pilot studies¹¹⁹ is explicitly in line with current literature on trial design.

Main Trial

General Data Analytic Strategy

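### Main trial, Hypothesis 1a: the hypothesis contrasts rewards with non-rewards, but the primary model takes only the response to rewards, and no win-minus-loss score is defined

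*Combined protocol and SAP*

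**What the plan says.** The hypothesis appears in the same form under Aims and Hypotheses (Main Trial, Aim 1) and under Analysis Plan, Main Trial, Specific Analyses: "Active iTBS relative to sham will increase the amplitude of the RewP/delta power to rewards compared to non-rewards". In Specific Analyses the next sentence gives the model: "GLMM will model the change in amplitude of the RewP/delta power to rewards as a function of iTBS condition", with random effects for repeated measures.

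The only differencing stated for the RewP is over time. The opening paragraph of Specific Analyses says: "Outcome variables will be modeled as difference scores to account for the pre/post design (i.e., post-iTBS minus pre-iTBS").

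The main trial's EEG Measures paragraph treats the two components differently. For the RewP: "Both ERP (mean amplitude) and TFA approaches will be used to analyze the RewP". For the LPP: "a difference score (cocaine minus pleasant) will be used to assess LPP bias". The Doors Task delivers wins and losses on half the trials each, so loss data are collected.

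Sample Size and Power Analysis names Hypothesis 1a as the hypothesis that sets the sample size: N = 75, r = 0.50 among repeated measures, two-tailed alpha 0.05, and 80% power at Cohen's f = 0.149.

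**The concern.** The hypothesis concerns a difference between two feedback types. The model's outcome is the change in one of them. These are different estimands and can lead to opposite conclusions.

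- **A positive result need not support the hypothesis.** If active iTBS moves win and loss amplitudes by the same amount, a rewards-only model would report increased reward sensitivity although the contrast is unchanged. Shifts common to active and sham days cancel in the comparison of conditions; the risk is shifts specific to active stimulation.
- **A real change in the contrast can be missed.** If part of the change comes from the response to losses, the rewards-only outcome sees only the remainder.

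The section headed Probability and Inference tests at alpha 0.05 the primary outcomes named in Specific Analyses, so this is where the primary outcome is fixed. While hypothesis and model disagree, an analyst could follow either one, and could choose after seeing the data.

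**Working it through.** **1. Does any other text supply the contrast?**

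| Place | What it says about scoring |
|---|---|
| Specific Analyses, opening paragraph | Differences are post minus pre; feedback type is not mentioned |
| Specific Analyses, Hypothesis 1a model | Change in response to rewards, by iTBS condition only |
| Main-trial EEG Measures, RewP | Mean amplitude and time-frequency analysis; no contrast |
| Main-trial EEG Measures, LPP | Cocaine minus pleasant |
| Background; pilot description of the Doors Task | The component is more positive to wins than to losses: a description, not a scoring rule |
| Summary of Significance | "a decreased RewP to wins and increased LPP to cocaine cues are potential targetable physiological patterns for TMS manipulation" |

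The last row attaches the RewP to wins alone, so the documents do not use the term consistently for a built-in win-minus-loss difference. Delta power, which EEG Measures names as the focus of the main hypotheses, has no subtraction defined anywhere.

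**2. The plan's own power figure.** For a within-subject factor with m = 3 conditions, λ = f²·N·m/(1 − r), with df = (m − 1, (N − 1)(m − 1)) = (2, 148).

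With f = 0.149, N = 75 and r = 0.50: λ = 0.149² × 75 × 3 / 0.5 = 9.99, and power is 80.7%. This reproduces the stated 80%. Treating the factor as 3 conditions × 2 feedback types (m = 6) gives 94.9%, which does not. The plan therefore assumed one score per condition, but the figure cannot show whether that score is wins only or wins minus losses.

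**3. Size of the discrepancy.** Assumptions: shifts are in SDs of the pre-to-post change in win amplitude; the shift is the same at both active sites; win and loss changes have equal SDs; between-day r = 0.50 for either score. With condition means (0, d, d), f = d·√2/3.

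*(a) Wins and losses shift equally, so the contrast is truly zero.*

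| d (SD) | f | λ | Rewards-only significant | Win-minus-loss significant |
|---|---|---|---|---|
| 0.1 | 0.047 | 1.0 | 13% | 5% |
| 0.2 | 0.094 | 4.0 | 41% | 5% |
| 0.3 | 0.141 | 9.0 | 76% | 5% |

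A simulation of 20,000 trials per cell agreed: 0.13, 0.41 and 0.76 for rewards-only, and 0.048 to 0.053 for win-minus-loss.

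*(b) The contrast truly changes by 0.30 SD.* The rewards-only outcome sees only the share carried by wins.

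| Share carried by wins | d seen by the rewards-only model | Rewards-only power |
|---|---|---|
| All | 0.30 | 76% |
| Half | 0.15 | 25% |
| None | 0 | 5% |

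The win-minus-loss score has SD √(2(1 − c)) relative to the win score, where c is the win-loss correlation of the change scores. Its power does not depend on the share.

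| c | Relative SD | Standardised d | Win-minus-loss power |
|---|---|---|---|
| 0.3 | 1.18 | 0.254 | 61% |
| 0.5 | 1.00 | 0.300 | 76% |
| 0.7 | 0.77 | 0.387 | 94% |

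**The case against.** The strongest reply is that the model sentence is shorthand. It follows the full hypothesis directly and repeats most of its wording, and several descriptions in the document characterise the RewP by how wins differ from losses. That reading is possible. It does not settle the matter, because none of those descriptions is a scoring rule, and the same EEG Measures paragraph that spells out the LPP contrast gives none for the RewP.

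A second reply is that if losses carry the whole change, the response to rewards has not risen, so missing it may be consistent with the hypothesis. This has some force for the extreme case (the 5% row). It does not touch the shared case (25% power) or the equal-shift case.

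Third, the percentages rest on assumed shifts and correlations, and on the three-condition F test rather than a direct active-versus-sham contrast. Both points are correct. The F test was used because the plan's power calculation uses it. A one-degree-of-freedom contrast of the two active days against sham gives about 17%, 51% and 84% for the equal shifts in (a), so the conclusion is the same.

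Fourth, the stated power is not shown to be wrong. That is also true: f is standardised and the figure reproduces. What is missing is a statement of which score f and r describe.

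Finally, the main trial is registered separately from the pilot and its recruitment awaited funding. That makes the correction easier; it does not remove the need for it.

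**Conclusion.** The concern holds. As written, the primary model for Hypothesis 1a estimates the change in response to rewards, while the hypothesis is about rewards relative to non-rewards. The mismatch is evident from the text and does not depend on any numerical assumption.

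Its possible size does. Under the assumptions above, the rewards-only model would be significant 13% to 76% of the time when the contrast is truly unchanged, and its power for a 0.30 SD change in the contrast would range from 76% down to 5% according to how much of the change wins carry. The documents contain no RewP SD, no win-loss correlation and no evidence on whether iTBS affects the response to losses, so these are illustrations, not predictions.

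Because this is the hypothesis that sets the sample size, it should be corrected before any main-trial analysis. Two related points are minor:

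- The pilot's Aim 1 model also leaves the RewP outcome undefined, although the pilot states no reward versus non-reward hypothesis.
- Exploratory Hypothesis 2b in Specific Analyses speaks of an increase in LPP bias. Its own explanation (pleasant above cocaine) is a decrease on the cocaine-minus-pleasant score.

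**What to change.** - **Outcome.** Define the primary RewP and delta-power outcomes as wins minus losses at each EEG session, then post minus pre. Equivalently, keep both feedback types in the model and test the interaction of feedback type with iTBS condition. Report win and loss amplitudes separately as supportive results.
- **Alternative.** If rewards only is intended, remove the comparison with non-rewards from Hypothesis 1a in both places, and do not describe the result as a reward versus non-reward effect.
- **Power.** State which score f = 0.149 and r = 0.50 describe, and justify the assumed SD and between-day correlation for that score.
- **Minor.** Give the same RewP definition in the pilot; with a win-minus-loss score its time and location model needs no extra term. Reword Hypothesis 2b as a greater decrease in the cocaine-minus-pleasant score.

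The cost is SAP wording and a restated power calculation; no new data are needed. The downside is that a difference score may have a different SD (1.18, 1.00 or 0.77 times that of the win score for c = 0.3, 0.5 or 0.7) and a lower correlation between days. At f = 0.149 and N = 75, power falls from 81% at r = 0.50 to 73%, 65% or 59% at r = 0.4, 0.3 or 0.2.
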